Study Title: 4DCT Imaging for Improved Diagnosis and Treatment of Wrist Ligament Injuries

NCT#: NCT03193996

Document Date: 13 September 2022

General Study Information

Principal Investigator: [name]

Study Title: 4DCT Imaging for improved diagnosis and treatment of wrist ligament injuries

Protocol version number and date: 5.0, 09/13/2022

Research Question and Aims

Specific Aim #1: Establish the relationship between SLIL injury and 4DCT metrics in vitro. Cadaveric specimens will be scanned using our 4DCT approach and location of scapholunate gapping determined during simulated wrist movements, following the intact condition and each of the sequential cuts to the palmar, membranous, dorsal SLIL, and secondary ligament stabilizers. The scientific premise for this aim is our pilot cadaveric and patient imaging¹⁷ using 4DCT, as well as supporting literature^{2, 22-29}.

Hypothesis 1: The size and location of gapping (palmar or dorsal) at the scapholunate joint during wrist motion is related to location of ligament injury.

Specific Aim #2: Assess the location of SLIL injury in patients using 4DCT metrics. Patients with unilateral SLIL injury will be scanned pre-surgically using 4DCT during wrist movement to characterize scapholunate gapping and predict injury location. Patients will have arthroscopic confirmation of location of ligament injury. The scientific premise for this aim is our pilot work that established a relationship between unilateral SLIL injury and 4DCT metrics¹⁷.

Hypothesis 2: The location of ligament injury can be predicted by the size and location of palmar or dorsal gapping at the scapholunate joint.

Specific Aim #3: Determine the effect of targeted treatment of SLIL injury on post-surgical outcomes, as assessed using 4DCT metrics. Surgeons will assess scapholunate gapping and document a treatment plan to address the specific injury. Then, 4DCT imaging findings will be compared with arthroscopic evaluation. 4DCT will also be performed at 1 year postoperatively, and radioscapoid contact patterns will be assessed during wrist movement to determine if normal patterns of motion are restored. The scientific premise for this aim is reports of unsuccessful treatment resulting in OA at the radioscapoid joint^{5-9, 20}.

Hypothesis 3a: Pre-operative treatment planning using 4DCT will provide equivalent findings as arthroscopic observations.

Hypothesis 3b: At one year post surgery, radioscapoid metrics for the injured wrist will mirror the contralateral wrist.

Study Design and Methods

Methods:

4DCT Imaging

A non-FDA approved research CT scanner (Siemens NAEOTOM Alpha syngo CT VA40) or a dual source CT scanner will be used for imaging. Two independent but identical x-ray tubes are mounted on a rotating gantry at a 94 degree offset, with respective detector arrays opposing them. 4D (3D + time) CT imaging acquires high-temporal resolution, continuous or intermittent images over the width of the detector array in the superior-inferior direction. A bilateral static CT scan of the wrist will be first performed. After that, two dynamic CT scans (4DCT) will be performed while patients are performing flexion-extension and radial-ulna deviation. For the dynamic scans, sequential, dual-source scanning mode is used which is similar to CT perfusion imaging. In this mode, imaging data of a moving joint are continuously acquired without table translation. Two seconds of data will be acquired for each movement (full cycles of flexion-extension and radial-ulnar deviation).

Eighteen image volumes will be reconstructed over the 2 second cycle using the commercially implemented dual-source cardiac reconstruction algorithm, resulting in a voxel dimension of 0.234 x 0.234 x 0.600 mm. 3D images of each of the 18 volumes, which are evenly distributed (temporally) across the motion cycle, will be generated using volume rendering techniques (VRT) and 4D movies will be made using the scanner's image processing workstation. All images will be stored in DICOM format for determination of metrics and biomarkers. All of the DICOM volumes will be processed using Analyze and existing software previously developed by our study team in Matlab (Mathworks, Inc.) platforms.

Deidentified image datasets will be uploaded for public use to a publicly accessible server. The image datasets will be utilized in the development of the open-source code SlicerAutoscoper^M (SA^M) to simplify and improve image-based skeletal tracking, facilitate the sharing of novel analysis algorithms, methodologies, and data, and hasten the translation to clinical implementation. The datasets will be further used to refine the software and validate its performance, and to train new users of this open-source software.

Aim 1:

40 cadaveric forearm/hand specimens will be obtained from the Mayo Clinic Anatomical Bequest program. 10 will be used to refine the ligament injury model and 30 will be used as follows. The specimens will undergo radiographic screening and will be excluded from the study if they have evidence of fracture, bony trauma, significant arthritic changes, or previous surgeries. The tendons will be loaded. The remaining soft tissues will be dissected from the proximal ulna and radius. Polymethylmethacrylate (PMMA) resin will be used to affix the proximal radius and ulna in a circular acrylic fixture. The custom wrist motion simulator was designed to generate muscle-assisted flexion-extension and radial-ulnar deviation movements and is CT-compatible. Each tendon will be dynamically loaded with a constant 10 N, maintained throughout the movement in the following conditions: wrist flexion-extension and radial-ulnar deviation. The hand will be fixed in a grip that is connected to a programmable linear actuator. The linear actuator drives the grip back-and-forth along the x-axis with free-motion along the z-axis. The linear actuator will be programmed to allow the wrist to perform a full radial-ulnar

**Table 1. In vitro testing conditions.**

All ligaments intact (15M, 15F)
Volar SLIL cut
Membranous SLIL cut
Dorsal SLIL cut
Radioscaphocapitate cut
Long radiolunate cut

or flexion-extension motion at 30 deg/sec which simulates in vivo wrist motion speeds. A motion cycle is approximately 2 seconds. The wrist will be cycled 100 times in flexion-extension prior to each testing condition. A static CT image will be acquired in the neutral posture. Then, each wrist will be imaged using 4DCT during flexion-extension and radial-ulnar deviation, in the following conditions: intact (control), volar SLIL cut, membranous SLIL cut, dorsal SLIL cut, radioscapheocapitate ligament cut, and long radiolunate ligament cut (**Table 1**).

Aim 2:

4DCT scanning will be performed bilaterally on 60 patients (30 males, 30 females) with unilateral SLIL injury who are scheduled to undergo a surgical intervention. In addition, patients will have pre-surgical volar and dorsal arthroscopic confirmation of ligament injury, categorized by Geissler and European Wrist Arthroscopy Society (EWAS) classifications; video recording of the arthroscopy will be obtained for later analysis. PRWE and VAS questionnaires will be completed at the 4DCT visit for the injured wrist and the Total PRWE Score (sum of pain and function subscales) and composite change in VAS score used in the analysis. 4DCT wrist data will be obtained while the subjects perform flexion-extension and radial-ulnar deviation. The dynamic image sequence will be processed with existing software tools to obtain metrics describing the interosseous distances between the articular surfaces of the scaphoid, lunate, and radius, during the movement cycles. Given the difficulty of diagnosing SLIL injury, the uninjured contralateral wrist is often used as a “control” for comparison by physicians; therefore, the difference in right/left metrics will be used in the study.

Aim 3:

The same 60 patients (see Aim 2) will be evaluated. Surgeons will assess pre-surgical scapholunate interosseous distances (quantified using 4DCT in Aim 2) and document a treatment plan to address the particular injury. Subsequently, 4DCT-based treatment plans will be compared with arthroscopic evaluation (obtained in Aim 2); any existing wrist x-rays (e.g. AP, lateral, stress views) and MRIs may be used in this comparison as well. The surgeon will then select and perform the targeted surgical intervention based on both 4DCT and arthroscopic findings. 4DCT will be performed, and the PRWE and VAS completed by patients at 1 year postoperatively; quantification of radioscapheocapitate contact patterns will be assessed during bilateral wrist flexion-extension and radial-ulnar deviation to determine if normal patterns of motion are restored.

(1a) This is a multisite study involving Mayo Clinic and non Mayo Clinic sites. *When checked, describe in detail the research procedures or activities that will be conducted by Mayo Clinic study staff.*

(1b) Mayo Clinic study staff will be engaged in research activity at a non Mayo Clinic site. *When checked, provide a detailed description of the activity that will be conducted by Mayo Clinic study staff.*

Subject Information

Target accrual: 60 subjects

Subject population (children, adults, groups):

Subjects with diagnosed symptomatic unilateral scapholunate instability for whom surgery is indicated, will be recruited.

Inclusion Criteria:

The following Inclusion criteria will apply to the patients with unilateral scapholunate instability. In the symptomatic wrist, they will have:

- 1) point tenderness over the dorsal aspect of the scapholunate joint, and one or more of the following:
- 2) positive Watson shift sign (Watson et al., J Hand Surg Am, 1988; 13:657-60);
- 3) suspected pathology on previous fluoroscopy or MRI

In the contralateral wrist, they will have an absence of scapholunate symptoms on physical exam.

Exclusion Criteria:

Exclusion criteria which will be applied to both wrists are as follows:

- 1) previously-diagnosed rheumatological conditions or connective tissue diseases;
- 2) inability to be appropriately positioned in the scanner for the imaging;
- 3) congenital malformations of the wrist or forearm;
- 4) diagnosed wrist osteoarthritis
- 5) age under 18 or over 60.

Research Activity

Check all that apply and complete the appropriate sections as instructed.

1. **Drug & Device:** Drugs for which an investigational new drug application is not required. Device for which (i) an investigational device exemption application is not required; or the medical device is cleared/approved for marketing and being used in accordance with its cleared/approved labeling. (Specify in the Methods section)
2. **Blood:** Collection of blood samples by finger stick, heel stick, ear stick, or venipuncture.
3. **Biological specimens other than blood:** Prospective collection of human biological specimens by noninvasive means that may include: urine, sweat, saliva, buccal scraping, oral/anal/vaginal swab, sputum, hair and nail clippings, etc.
4. **Tests & Procedures:** Collection of data through noninvasive tests and procedures routinely employed in clinical practice that may include: MRI, surface EEG, echo, ultrasound, moderate exercise, muscular strength & flexibility testing, biometrics, cognition testing, eye exam, etc. (Specify in the Methods section)
5. **Data (medical record, images, or specimens):** Research involving use of existing and/or prospectively collected data.

6. **Digital Record:** Collection of electronic data from voice, video, digital, or image recording. (Specify in the Methods section)
7. **Survey, Interview, Focus Group:** Research on individual or group characteristics or behavior, survey, interview, oral history, focus group, program evaluation, etc. (Specify in the Methods section)

NIH has issued a *Certificate of Confidentiality* (COC). *When checked, provide the institution and investigator named on the COC and explain why one was requested.* _____

Review of medical records, images, specimens – Category 5

For review of existing data: provide a date range or an end date for when the data was generated. The end date can be the date this application was submitted to the IRB. Example: *01/01/1999 to 12/31/2015* or all records through *mm/dd/yyyy*.

Date Range:

Check all that apply (data includes medical records, images, specimens).

(5a) Only data that exists before the IRB submission date will be collected.

(5b) The study involves data that exist at the time of IRB submission **and** data that will be generated after IRB submission. Include this activity in the Methods section.

Examples

- The study plans to conduct a retrospective chart review and ask subjects to complete a questionnaire.
- The study plans to include subjects previously diagnosed with a specific disease and add newly diagnosed subjects in the future.

(5c) The study will use data that have been collected under another IRB protocol. Include in the Methods section and enter the IRB number from which the research material will be obtained. *When appropriate, note when subjects have provided consent for future use of their data and/or specimens as described in this protocol.*

Enter one IRB number per line, add more lines as needed

Data Specimens Data & Specimens _____

Data Specimens Data & Specimens _____

Data Specimens Data & Specimens _____

(5d) This study will obtain data generated from other sources. Examples may include receiving data from participating sites or an external collaborator, accessing an external database or registry, etc. Explain the source and how the data will be used in the Methods section.

(6) Video audio recording: *Describe the plan to maintain subject privacy and data confidentiality, transcription, store or destroy, etc.*

HIPAA Identifiers and Protected Health Information (PHI)

Protected health information is medical data that can be linked to the subject directly or through a combination of indirect identifiers.

Recording identifiers (including a code) during the conduct of the study allows you to return to the medical record or data source to delete duplicate subjects, check a missing or questionable entry, add new data points, etc. De-identified data is medical information that has been stripped of all HIPAA identifiers so that it cannot be linked back to the subject. De-identified data is **rarely** used in the conduct of a research study involving a chart review.

Review the list of subject identifiers below and, if applicable, check the box next to each HIPAA identifier being recorded at the time of data collection or abstraction. Identifiers apply to any subject enrolled in the study including Mayo Clinic staff, patients and their relatives and household members.

Internal refers to the subject's identifier that will be recorded at Mayo Clinic by the study staff.

External refers to the subject's identifier that will be shared outside of Mayo Clinic.

Check all that apply:	INTERNAL	EXTERNAL
Name	x	
Mayo Clinic medical record or patient registration number, lab accession, specimen or radiologic image number	x	
Subject ID, subject code or any other person-specific unique identifying number, characteristic or code that can link the subject to their medical data	x	x
Dates: All elements of dates [month, day, and year] directly related to an individual, their birth date, date of death, date of diagnosis, etc.	x	
Note: Recording a year only is not a unique identifier.		
Social Security number	x	
Medical device identifiers and serial numbers		
Biometric identifiers, including finger and voice prints, full face photographic images and any comparable images		

Web Universal Resource Locators (URLs), Internet Protocol (IP) address numbers, email address	x	
Street address, city, county, precinct, zip code, and their equivalent geocodes	x	
Phone or fax numbers	x	
Account, member, certificate or professional license numbers, health beneficiary numbers		
Vehicle identifiers and serial numbers, including license plate numbers		
Check 'None' when none of the identifiers listed above will be recorded, maintained, or shared during the conduct of this study. (exempt category 4)	 None	 None

Data Analysis

Data Analysis Plan:

Aim 1:

Data from 15 male and 15 female cadaveric specimens will include the gap size across the normalized lunate surface in the volar/dorsal direction (with 0 = volar aspect and 1 = dorsal aspect of lunate articular surface) at the scapholunate joint. These values will be obtained for the intact condition and following each of the 5 ligament cuts for each of the 18 time steps (positions of the wrist) for both the radial-ulnar and flexion-extension motions. Spline curves will be fit to describe the gap size as a function of the normalized volar/dorsal position along the lunate surface, for each of the 18 time steps in all conditions (intact and ligament cut), for the male and female specimens. We will compare the gap size and location between the intact and ligament cut conditions to establish a relationship between the 5 ligament cut conditions and the size and location of gapping at the scapholunate joint for males and females. We will also fit spline curves to collapsed data such as the maximum gap size from all of the 18 time steps, average gap size, root mean square error of gap size, maximum minus minimum of gap size, and explore their ability to identify ligament injury. In this aim, each subject will serve as their own control and emphasis will be on the differences in gap sizes between the cut and intact conditions. In patients (Aims 2 and 3) the emphasis will expectedly be on the differences between the injured and contralateral wrist. We will use resampling methods such as cross-validation and bootstrap to assess accuracy of the derived diagnostic algorithms. Analysis will be based on all data from both male and female specimens, including a main effect to distinguish between the sexes, if indicated by the data. Secondary analyses will include analyzing male and female data separately, and examining for potential differences (interactions).

Aim 2:

Normalized volar/dorsal location of the gapping at the scapholunate joint for the 30 male and 30 female subjects obtained pre-surgically will be analyzed using the algorithm developed in Aim 1 to infer if and where any ligament injuries have occurred. Additionally, we will have findings on presence or absence of ligament injuries from volar and dorsal arthroscopy on each subject pre-surgically. Finally we will have PRWE and VAS data for each patient. The primary assessment will be of the percent of patients for whom the 4DCT and arthroscopic findings agree. Secondarily, we will fit models including PRWE and VAS to inform of thresholds for injury to see if this may improve prediction. These analyses will be repeated by sex, and other subgroups that may alter the relation between size and location of any gapping, and ligament injury, e.g. height, weight. In an exploratory manner, we will repeat analyses similar to Aim 1 to determine if the diagnostic model derived in Aim 1 might

be improved upon. With our sample of 60 patients, and the hypothesized agreement between the 4DCT of 95%, we will have 83% power to identify an agreement of 0.85 or less, using a chi-square test.

Aim 3:

Magnitude and direction of radioscapheoid contact center migration, bilaterally, will be analyzed during the 18 time steps during both radial-ulnar deviation and flexion-extension pre-surgically and 1-year post-surgically. Additionally, pre- and post-surgical PRWE and VAS will be analyzed. The change from pre- to post-surgical migration of the contact center in the injured limb as a percent normalization relative to the pre-surgical contralateral limb values will be determined and described using the t-distribution. Similarly, the change in pre- to post-surgical PRWE and VAS values will be compared. These analyses will be repeated by sex, and other subgroups that become apparent during the study. With our sample of 60 patients, and the hypothesized agreement between the 4DCT of 95%, we will have 83% power to identify an agreement of 0.85 or less, using a chi-square test. With a sample size of 60, using a two-sided size 0.05 t-test, we will have 80% power to detect an effect size of 0.37 for the analysis of quantitative outcomes.

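### In patients who move the wrist themselves, a time step does not fix wrist position, yet the plan states no angle measurement, angle registration or common arc for the Aim 2 and Aim 3 comparisons

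*Combined protocol and SAP*

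**What the plan says.** **Acquisition.** Methods, 4DCT Imaging, describes "18 volumes, which are evenly distributed (temporally) across the motion cycle", with two seconds of data for each movement. The spacing is in time, not in wrist angle.

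**Cadavers.** Methods, Aim 1: "The hand will be fixed in a grip that is connected to a programmable linear actuator". The actuator is set to 30 deg/sec, and "A motion cycle is approximately 2 seconds". Data Analysis Plan, Aim 1, obtains gap values "for each of the 18 time steps (positions of the wrist) for both the radial-ulnar and flexion-extension motions" and fits a spline along the lunate surface at each step. It also plans curves on summaries over the steps: maximum, average, root mean square error, and maximum minus minimum. The only normalized axis is the volar/dorsal position on the lunate.

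**Patients.** Methods, Aim 2: "4DCT wrist data will be obtained while the subjects perform flexion-extension and radial-ulnar deviation". Right/left differences are used. Data Analysis Plan, Aim 2, applies the Aim 1 algorithm to the patients, and the primary assessment is the percentage in whom 4DCT and arthroscopy agree. In Data Analysis Plan, Aim 3, contact-center migration "will be analyzed during the 18 time steps during both radial-ulnar deviation and flexion-extension", before surgery and 1 year after. The pre-to-post change in the injured limb is scaled to the pre-surgical contralateral values.

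**Not stated for patients.** Pacing, a guide, a start posture, a trigger, a target arc, measurement of wrist angle, registration of curves to angle, or range or speed as a covariate.

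**The concern.** Scapholunate gap and radioscaphoid contact are studied during motion because they may change with posture. A comparison of two wrists, two visits, or a cadaver with a patient therefore isolates the joint only if posture is the same or is accounted for. The actuator largely ensures this in Aim 1. Nothing stated ensures it in patients.

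Three comparisons are exposed:

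1. **Injured against contralateral.** A painful or stiff wrist may cover less arc or lag behind the other, which could produce a side difference without any difference in ligament behaviour.
2. **Cadaver against patient.** An algorithm learned on an actuator-driven sweep is applied to a voluntary one. This feeds the primary assessment of Aim 2.
3. **Before against after surgery.** Contact-center migration depends on the arc travelled, so a changed arc at 1 year could be read as changed migration. Hypothesis 3b rests on this result.

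**Working it through.** **1. The plan's power figures, for reference.** A one-sample or paired t-test with N = 60, effect size 0.37, two-sided 0.05 and 59 degrees of freedom gives 80.5% power (80% stated). For agreement, with null 0.95, alternative 0.85 and two-sided 0.05 (sidedness assumed), power = Φ[(0.10 − 1.96·√(0.95·0.05/60)) / √(0.85·0.15/60)] = Φ[(0.10 − 0.0551)/0.0461] = 83.5% (83% stated). Both reproduce, and neither changes because of this point.

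**2. Geometry from the documents.** Inputs from Methods: 30 deg/sec, a cycle of about 2 s, 18 volumes.
- Travel per cycle: 30 × 2 = 60 degrees.
- If the cycle is there and back, the arc is 30 degrees, a half-arc of 15 degrees.
- Spacing of volumes: 2/18 = 0.11 s, or 60/18 = 3.3 degrees at constant speed.

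**3. Posture mismatch at the same step number.** Assumed, since the documents give no patient range or timing: sinusoidal motion, half-arc A of 15 to 60 degrees, lag 0.1 s (just under one step), second arc 80% of the first.

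Reference a(t) = A·sin(πt); comparator b(t) = s·A·sin(π(t − lag)); |a − b| at 18 equally spaced times over 2 s. Mean (maximum), in degrees:

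| Half-arc A | Lag 0.1 s only | 20% smaller arc only | Both |
|---|---|---|---|
| 15 | 3.0 (4.6) | 1.9 (3.0) | 3.3 (5.1) |
| 30 | 5.9 (9.3) | 3.8 (5.9) | 6.6 (10.3) |
| 60 | 11.9 (18.5) | 7.6 (11.8) | 13.2 (20.6) |

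Cross-check for both together: a − b is a sinusoid of amplitude A·√(1 + s² − 2s·cos(π·lag)) = A·√(1.64 − 1.6 × 0.951) = 0.344A, with mean absolute value (2/π) × 0.344A = 0.219A. At A = 15 this is 5.2 and 3.3 degrees; at A = 60 it is 20.6 and 13.1, in line with the table.

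**4. Collapsed summaries.** Over a full cycle a pure lag only reorders the postures, so the maximum, average and range over steps hardly change. A smaller arc removes end-range postures, and a change of speed alters the time spent at each posture. Both remain in the summaries.

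**5. What a posture-only shift would do to the t-test (assumed sizes).** With the test in step 1 and no true joint change, a systematic shift of 0.1, 0.2 or 0.3 SD of the metric is declared significant in 11.9%, 33.2% or 62.8% of trials instead of 5%. The documents do not show which of these shifts, if any, would occur.

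**6. Where the arithmetic stops.** No gap-per-degree or migration-per-degree figure is given, so degrees cannot be turned into millimetres or into misclassified patients.

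**The case against.** The sentence equating steps with positions, and the rule of one spline per step, are written for cadaver specimens, where they are sound. No sentence says that step k of one wrist is subtracted from step k of the other: Aim 2 refers only to right/left metrics, and the final form of the algorithm is open. The collapsed summaries need no step matching. Scanning is bilateral, and if both wrists move in one acquisition, left/right lag is limited. The actuator speed is said to simulate in vivo motion, which points to the low end of the degree range. In Aim 3 the question is whether normal motion is restored, so lost arc may be part of the outcome, and trimming to a common arc could hide it.

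Much of this stands. It clears the within-specimen cut/intact comparison, weakens the lag component, requires the 15-degree case in the range, and means the matched-angle analysis must not replace the full-arc result in Aim 3. It does not remove the point. Data Analysis Plan, Aim 3, does use the 18 steps in patients at both visits. The Aim 1 algorithm does carry over to patients. Moving both wrists together would not equalize their arcs, and the collapsed summaries remain open to arc and speed.

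A reader might infer that every time-indexed comparison in the study is invalid, or that the plan prescribes step-by-step subtraction between wrists. The documents support neither.

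**Conclusion.** The concern holds for the patient comparisons and for the transfer from cadaver to patient. Differences in arc, speed or phase could enter the Aim 2 classification and the Hypothesis 3b result, and the plan states no means of separating them from joint change. The illustrative mismatch is a mean of about 3 to 13 degrees (maximum 5 to 21). It rests on sinusoidal motion, a 0.1 s lag, a 20% smaller arc, and half-arcs from 15 degrees (implied by the cadaver speed and cycle) to 60 degrees (assumed).

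It would be tempting to conclude that the results will be biased, or biased towards apparent normalization after surgery. The documents do not support that: they give no patient arc and no relation between posture and gap or migration, so neither direction nor size is known. Nor is any stated sample size or power figure wrong on this account. The point merits a change because the exposure follows from the stated index and the remedy uses images already planned.

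**What to change.** For patient scans, amend the analysis plan as follows.

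- Compute wrist angle at each of the 18 volumes from the bones already imaged, for example the distal carpal row relative to the radius.
- Express gap and contact metrics as functions of wrist angle and direction of motion. Put the cadaver curves on the same angle scale so that the Aim 1 algorithm transfers.
- Compare injured with contralateral, and before with after surgery, at matched angles over the arc common to both.
- Report arc and speed for each wrist and visit.
- Keep the full-arc, time-step and collapsed-summary results alongside, so that lost motion in Aim 3 stays visible as a finding.

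Cut/intact comparisons within a cadaver need nothing beyond the common angle scale.

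**Cost.** Plan wording and extra image processing; no new scans and no change in N. End-range data outside the common arc leave the matched comparison, which is why the full-arc results should stay beside it.

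### Does Aim 2's percent agreement between 4DCT and arthroscopy need a written match rule and a base-rate comparator before it can be interpreted?

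*Combined protocol and SAP*

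**What the plan says.** Under Aim 2 of the Data Analysis Plan the primary measure is given in one sentence: "The primary assessment will be of the percent of patients for whom the 4DCT and arthroscopic findings agree". The 4DCT side applies the Aim 1 algorithm "to infer if and where any ligament injuries have occurred". The arthroscopic side is described there as "findings on presence or absence of ligament injuries from volar and dorsal arthroscopy on each subject pre-surgically", while Methods, Aim 2 says the injuries will be "categorized by Geissler and European Wrist Arthroscopy Society (EWAS) classifications". The sample size statement hypothesizes 95% agreement in 60 patients and adds that "we will have 83% power to identify an agreement of 0.85 or less, using a chi-square test".

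The algorithm comes from Aim 1, which sets out to "establish a relationship between the 5 ligament cut conditions and the size and location of gapping at the scapholunate joint". Methods, Aim 1 lists those conditions after the intact state as "volar SLIL cut, membranous SLIL cut, dorsal SLIL cut, radioscapheocapitate ligament cut, and long radiolunate ligament cut". Specific Aim #1 makes clear that the cuts are sequential. The Aim 2 patients are those "with unilateral SLIL injury who are scheduled to undergo a surgical intervention". Specific Aim #2 says that arthroscopy will confirm where the ligament is injured, and Hypothesis 2 is that 4DCT gapping predicts that location.

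**The concern.** The two sides of the comparison are described in different terms. One yields a location inferred by an algorithm trained on six states; the other yields presence or absence from two views, or a grade in one of two classifications. No section links them. Nor is it said whether a patient with two injured sites, one of them correctly identified, counts as agreement.

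Two consequences would matter. First, the same imaging performance could pass or fail the 95% value depending on the rule, and a rule chosen after seeing the data could decide the conclusion. Second, patients are recruited because injury is already suspected. If one pattern dominates, or if only presence is scored, high raw agreement may say little about what the imaging contributes, and no base-rate figure is planned to show this.

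**Working it through.** **Inputs.** From the Data Analysis Plan, Aim 2: n = 60, p0 = 0.95, p1 = 0.85, chi-square test, power 83%. The significance level is not given for this test; two-sided 0.05 is assumed, as in the t-test sentence under Aim 3.

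**1. The plan's own figure.** Power = Φ((|p0 − p1| − 1.96·√(p0(1 − p0)/n)) / √(p1(1 − p1)/n)).
- √(0.95 × 0.05/60) = 0.0281 and √(0.85 × 0.15/60) = 0.0461.
- (0.10 − 1.96 × 0.0281)/0.0461 = 0.973, and Φ(0.973) = 0.835.

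The stated 83% is reproduced with 95% as the null value.

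**2. Where the test rejects.** χ² = (x − 57)²/(60 × 0.95 × 0.05) = (x − 57)²/2.85.
- x = 53: 5.61, p = 0.018.
- x = 54: 3.16, p = 0.076.
- x = 60: 3.16, p = 0.076.

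It rejects at 53 or fewer agreements and never on the high side. Exact power at 0.85 is P(X ≤ 53) = 81.5%; exact size at 0.95 is 3.0%.

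**3. How far a match rule could move the result.** Assume, as no section does, 95% accuracy at each of k sites and a rule requiring all k to match. With independent errors the patient-level rate is 0.95^k. With errors that never coincide it is 1 − 0.05k; with errors that always coincide it is 0.95.

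| k | Independent rate | P(reject), independent | Possible range of rate |
|---|---|---|---|
| 2 | 0.9025 | 37% | 0.90–0.95 |
| 3 | 0.857 | 77% | 0.85–0.95 |
| 5 | 0.774 | 99% | 0.75–0.95 |

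The plan's 95% is a percent of patients. Read as an exact match over three independent sites, it corresponds to per-site accuracy of 0.95^(1/3) = 0.983; over two sites, 0.95^(1/2) = 0.975. The table therefore shows sensitivity to an input the plan never adopts. Independence is also doubtful: in sequential cuts each stage contains the previous ones, so the site calls are tied together.

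**4. Case mix under location scoring.** A rule that always names the commonest pattern agrees at that pattern's share. The chance that it reaches 54 of 60, and so is not rejected, is 0.02% at a 70% share, 3% at 80%, 18% at 85% and 61% at 90%. The shares are assumed; the documents give none. In a simulation with true agreement of 95%, four patterns and errors unrelated to pattern, mean kappa was 0.90, 0.86, 0.83 and 0.76 at those shares. At the first two shares, agreement near 95% cannot easily be had without information. At 90% the raw percent is weaker evidence: the margin over the constant rule is 95 − 90 = 5 points.

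**5. Presence or location.** Specific Aim #2, Hypothesis 2 and the description of the algorithm's output all refer to where the injury is. The presence-or-absence phrase speaks of ligament injuries in the plural, seen from volar and dorsal views, and reads naturally as a finding for each ligament. Presence-only scoring is the less supported reading.

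**The case for a change.** The strongest opposing case is that an undefined primary measure invites a choice after the fact. Even on the location reading, the sites counted and the treatment of partial matches are open, and a lenient rule can only raise the percent. Writing the rule down costs little, and arthroscopy video is to be kept, so location can be scored without any new procedure. All of that is true, and the analysts do have to fix the definition before the two sets of findings are put together.

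It does not amount to a defect that a specific amendment would cure. The obvious remedy is to count agreement only when the inferred and arthroscopic sets of injured sites are identical. That leaves open whether two, three or five sites count, which is the choice that moves the table above most. It also fits the design awkwardly. If the algorithm can return only the stages of a sequential cutting model, an isolated dorsal injury lies outside its outputs, and strict set equality would score every such patient as a disagreement whatever the imaging showed. A more tolerant mapping may serve the hypothesis better, and that judgment needs the Aim 1 results.

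The base-rate argument also has some force, but only where one pattern is very common. Even then a formal comparison would do little: in the simulation, requiring the 95% interval for the margin over the constant rule to exclude zero had power 0.16 at a 90% share and true agreement of 95%, with a mean interval width of 18 points. It could only be a descriptive addition, which the analysts may report without a change to the plan.

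**Conclusion.** The plan leaves the scoring of agreement unwritten, but the unit, the target (location), the reference standard and both numerical values are stated, and the power is right (83.5% against the stated 83%). The swing from 3% to 82% rejection over three sites, or up to 99% over five, depends on a 95% per-site accuracy that the plan does not claim. Under location scoring, a rule with no information would match a 95% result at most 3% of the time for pattern shares up to 80%; above that, the raw percent should be read alongside the case mix, which the data will show. This is a definition that competent analysts settle when they build the mapping from the Aim 1 output to the arthroscopic record, before comparing the two. The conclusion assumes that they score location and do so before that comparison. It would be different if presence alone were scored, since that would not test Hypothesis 2.
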